18.1.1.2. Relationship to Study Medication

Relationship, as indicated by the Investigator, is classed as “unrelated”, “unlikely related”, “possibly related”, “probably related”, or “unknown” (increasing severity of relationship). A “related” TEAE is defined as a TEAE with a relationship to study treatment as “possibly related” or “probably related”. TEAEs with a missing or “unknown” relationship to study treatment will be regarded as “probably related” to study treatment. If a patient reports the same AE more than once within that SOC/ PT, the AE with the worst case relationship to study treatment will be used in

Document: \\ieedc-vnasc01\BIOSdata\F2G\F901318\ [Redacted]
Author: [Redacted] Version Number: 3.0
Version Date: 06Apr2023
Template No.: CS_TP_BS016 Revision 6 Reference: CS_WI_BS005
Effective Date: 02Dec2019

the corresponding relationship summaries.

18.1.2. TEAEs LEADING TO DISCONTINUATION OF STUDY TREATMENT

TEAEs leading to permanent discontinuation of study treatment will be identified by “Action taken with study treatment” on the AE eCRF page indicated as “Drug withdrawal”.

For TEAEs leading to discontinuation of study treatment, summaries of incidence rates (frequencies and percentages) by SOC and PT will be prepared.

18.1.3. TEAEs LEADING TO STUDY WITHDRAWAL

TEAEs leading to premature study withdrawal will be identified by “Did the AE cause the patient to discontinue from the study” on the AE eCRF page indicated as “Yes”.

For TEAEs leading to premature study withdrawal, summaries of incidence rates (frequencies and percentages) by SOC and PT will be prepared.

18.1.4. SERIOUS ADVERSE EVENTS (INCLUDING DEATHS)

Serious adverse events (SAEs) are those events recorded as “Serious” on the AE page of the eCRF. A summary of serious TEAEs by SOC and PT, and a summary of serious TEAEs by SOC, PT and relationship to study treatment, will be prepared.

18.1.5. ADVERSE EVENTS LEADING TO DEATH

TEAEs leading to death are those events which are recorded as “Fatal” on the AE page of the eCRF. A summary of TEAEs leading to death by SOC and PT will be prepared.

18.1.6. ADVERSE EVENTS OF SPECIAL INTEREST

Adverse Events of Special Interest (AESIs) are to have “Yes” recorded as the response to the question “Does this event meet the definition of an Adverse Event of Special Interest” on the AE eCRF page.

The following events are classified as AESIs:

Document: \\weedc-vnasc01\BIOSdata\F2G\F901318\ [Redacted]
Author: [Redacted] Version Number: 3.0
Version Date: 06Apr2023
Template No.: CS_TP_BS016 Revision 6 Reference: CS_WI_BS005
Effective Date: 02Dec2019

[REDACTED]

F2G Ltd.
PROTOCOL F901318/0032

- [REDACTED]
- [REDACTED]
- [REDACTED]
- [REDACTED]
- [REDACTED]
- [REDACTED]

[REDACTED]

[REDACTED]

[REDACTED]

- [REDACTED]
- [REDACTED]

[REDACTED]

[REDACTED]

[REDACTED]

The CTCAE Grade definitions used for this study's AESIs are given in [Table 6](#) of protocol amendment 6.

AESIs are entered into the database by centres, and [REDACTED] Biostatistics will not programmatically verify the AEs meeting CTCAE criteria.

Summaries of Treatment emergent AESI incidence rates (number and percentage of patients) by AESI Category, SOC, PT (as determined by the investigator) will be prepared.

Summaries of Treatment emergent AESI incidence rates (number and percentage of patients) by AESI Category, SOC, PT and relationship (as determined by the investigator) will be prepared.

A summary of [REDACTED] by AESI Category, SOC, PT and relationship (as determined by the HAC) will be presented separately.

Document: \\weedc-vnasc01\BIOSdata\F2G\F901318 [REDACTED]
Author: [REDACTED] Version Number: 3.0
Version Date: 06Apr2023
Template No.: CS_TP_BS016 Revision 6 Reference: CS_WI_BS005
Effective Date: 02Dec2019

[REDACTED]

F2G Ltd.
PROTOCOL F901318/0032

AESIs leading to death are those AESI events which are recorded as “Fatal” on the AE page of the eCRF.

Summaries of Treatment emergent AESI incidence rates leading to death (number and percentage of patients) by AESI Category, SOC, PT and relationship (as determined by the investigator) will be prepared.

AESIs leading to permanent discontinuation of study treatment will be identified by “Action taken with study treatment” on the AE eCRF page indicated as “Drug withdrawal”.

Treatment emergent AESIs leading to permanent discontinuation of study treatment will be summarised by AESI Category, SOC and PT (as determined by the investigator).

AESIs leading to temporary discontinuation of study treatment will be identified by “Action taken with study treatment” on the AE eCRF page indicated as “Drug interrupted”.

Treatment emergent AESIs leading to temporary discontinuation of study treatment will also be summarised by AESI Category, SOC and PT.

Duration of study treatment discontinuation will be listed.

Histogram for number of [REDACTED] events by duration of Olorofim treatment (in Weeks) will be plotted.

18.1.7. CTC GRADING FOR ADVERSE EVENTS

AEs will be graded using the Common Toxicity grading (CTC) system as defined in:

Common Terminology Criteria for Adverse Events (CTCAE) v5.0.

CTC grades are assigned by the study centres and will not be programmatically verified by IQVIA Biostatistics.

18.1.8. TEAEs LEADING TO DOSE ADJUSTMENTS

TEAEs leading to dose adjustments will be identified by using the “Action taken with study treatment” question on the AE eCRF page, to which the answer is “Dose increased” or “Dose reduced”.

For TEAEs leading to dose adjustments, summaries of incidence rates (frequencies and percentages) by SOC and PT will be prepared.

Document: \\ieedc-vnasc01\BIOSdata\F2G\F901318 [REDACTED]
Author: [REDACTED] Version Number: 3.0
Version Date: 06Apr2023
Template No.: CS_TP_BS016 Revision 6 Reference: CS_WI_BS005
Effective Date: 02Dec2019

18.2. LABORATORY EVALUATIONS

Haematology and Serum Chemistry results from both the local and central laboratories will be included in the outputs for the study report. If both a local laboratory result and the central laboratory result exist for a visit, the central laboratory results of the two will be used in the summary tables and figures. All local and central laboratory results will be listed.

Urinalysis results from the local laboratory will be included in the outputs for the study report.

A list of laboratory assessments to be included in the outputs is included in protocol amendment 6, [Table 7](#).

Presentations will use SI Units. Central laboratory data will be provided to IQVIA Biostatistics in SI Units. IQVIA Biostatistics will convert local laboratory results to display in SI Units.

Quantitative laboratory measurements reported as “< X”, i.e. below the lower limit of quantification (BLQ), or “> X”, i.e. above the upper limit of quantification (ULQ), will be converted to X for the purpose of quantitative summaries, but will be presented as recorded, i.e. as “< X” or “> X” in the listings.

The following summaries will be provided for scheduled Haematology and Chemistry laboratory data:

- Table and box-and-whiskers plot of actual and change from baseline values descriptive statistics by visit (for quantitative measurements)
- Incidence of abnormal values according to normal range criteria
- Shift from baseline according to normal range criteria (for quantitative measurements and categorical measurements)
- Incidence of predefined treatment-emergent abnormalities, as defined by CTCAE criteria
- Shift from baseline according to CTC grading system
- Listing of Haematology and Chemistry laboratory data
-  as described in [section 18.2.4](#).
- The following will be presented in data listings:
 - Urinalysis data
 - Hepatologist review data

Document: \\weedc-vnasc01\BIOSdata\F2G\F901318\ 
Author:  Version Number: 3.0
Version Date: 06Apr2023
Template No.: CS_TP_BS016 Revision 6 Reference: CS_WI_BS005
Effective Date: 02Dec2019

F2G Ltd.
PROTOCOL F901318/0032

- Neutropenia status and absolute neutrophil count local laboratory results confirming neutropenia status

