 - r. Within 4 weeks prior to screening. See also Section 6.4.2.2: neutropenia is defined as $ANC < 0.5 \times 10^9/L$ [$< 500/mm^3$]. Neutropenia status will be recorded from the screening visit throughout the 4-week post treatment period. Neutropenic episodes supporting the Host Factor criteria of "Neutropenia" at the time of the initial diagnosis of the invasive fungal infection should also be reported. Absolute neutrophil count results from 4 weeks prior to screening through the patient's last study visit and any values supporting the Host Factor Criteria Neutropenia. Local Laboratory ANCs for all neutropenic episodes (defined as $ANC < 0.5 \times 10^9/L$ [$< 500/mm^3$]) from 4 weeks prior to screening up to the end of study and those that support a Host Factor Criteria of Neutropenia at the time of the initial diagnosis (which may be greater than 4 weeks prior to Screening). ANC results to cover the period from onset up to and inclusive of the first 2 consecutive ANC values $> 0.5 \times 10^9/L$ on consecutive days confirming resolution of the episode. When differentials are not performed due to insufficient WBCs, the total WBC count for the day should be recorded.
 - s. The Screening EQ-5D-5L questionnaire provides the baseline, and should be completed as close to the day prior to the start of treatment as is feasible.
 - t. Only in patients with abnormalities observed at main study phase EOT.

- u. See Table 7 and Appendix 3 for minimum list of tests to perform. Additional samples at unscheduled visits should also be taken if ALT/AST or bilirubin elevations occur (see Appendix 3). [REDACTED] Blood sampling for evaluation of liver function must always be consistent with the Liver Biochemistry Management Algorithm as described in Appendix 3.
- v. Systolic blood pressure, diastolic blood pressure, pulse rate and body temperature; body temperature should be measured via the same route throughout the study period. Vital signs should be measured before study drug administration.
- w. ECG on treatment should be performed between 30 min and 4 hours after dosing.
- x. [REDACTED]

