- Elevation of AST or ALT $> 3 \times$ ULN in temporal association with nausea, vomiting, anorexia, abdominal pain, or fatigue.

Treatment-emergent is defined as any event (scheduled or unscheduled) which started or worsened on or after the first dose of study drug or during the post-treatment FU. Treatment-emergent AEs which occur in the main study phase or FU will be presented in the study report; TEAEs which occur in the ET phase or post-ET FU will be presented in the report addendum.

In addition, figures and listings will be presented for possible treatment-emergent Hy's Law cases (patients with any elevated AST or ALT $> 3 \times$ ULN, ALP $< 2 \times$ ULN and associated with an increase in total bilirubin $\geq 2 \times$ ULN).

[REDACTED]

[REDACTED]

[REDACTED]

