6.4. RETESTS, UNSCHEDULED VISITS AND EARLY TERMINATION DATA

In general, for by-visit summaries, data recorded at the nominal visit will be presented. Unscheduled measurements will not be included in by-visit summaries but will contribute to the derived EOT/EOS value, or best/ worst case value where required (e.g. shift table).

In the case of a retest (same visit number assigned), the latest available measurement for that visit will be used for by-visit summaries.

Listings will include scheduled, unscheduled, retest and early discontinuation data.

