- If a CTCAE criterion does not consider change from baseline, to be evaluable the patient need only have one post-dose value recorded.

Document: \\weedc-vnasc01\BIOSdata\F2G\F901318\ [Redacted]
 Author: [Redacted] Version Number: 3.0
 Version Date: 06Apr2023
 Template No.: CS_TP_BS016 Revision 6 Reference: CS_WI_BS005
 Effective Date: 02Dec2019

[Redacted]

F2G Ltd.
PROTOCOL F901318/0032

In the event that a laboratory value does not comply with the CTCAE criterion, the laboratory value will be categorised as normal.

18.2.4. [Redacted]

[Redacted]

[Redacted]

[Redacted]

[Redacted]

[Redacted]

[Redacted]

[Redacted]

[Redacted]

Document: \\eedc-vnasc01\BIOSdata\F2G\F901318 [Redacted]

Author: [Redacted] Version Number: 3.0

Version Date: 06Apr2023

Template No.: CS_TP_BS016 Revision 6

Reference: CS_WI_BS005

Effective Date: 02Dec2019

[Redacted]

[REDACTED]

F2G Ltd.
PROTOCOL F901318/0032

[REDACTED]

[REDACTED]

[REDACTED]

[REDACTED]

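### SAP 18.2 confines the laboratory incidence and shift tables to scheduled samples, so a peak seen only on an unscheduled liver test may be missing from them

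*SAP*

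**What the plan says.** SAP section 18.2 opens its list of outputs with "The following summaries will be provided for scheduled Haematology and Chemistry laboratory data". Under that lead-in come the by-visit tables and box plots, incidence of values outside the normal range, normal-range shift, incidence of CTCAE-defined treatment-emergent abnormalities, shift by CTC grade, the listing, and a partly redacted item that points to section 18.2.4.

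Three other places bear on unscheduled results:

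- Protocol section 8.9.3: "Treatment-emergent is defined as any event (scheduled or unscheduled) which started or worsened on or after the first dose of study drug".
- SAP section 6.4 keeps unscheduled measurements out of by-visit summaries, but says that they "will contribute to the derived EOT/EOS value, or best/ worst case value where required (e.g. shift table".
- The protocol's main-phase schedule of events (section 4.1, Table 1, footnote u) says: "Additional samples at unscheduled visits should also be taken if ALT/AST or bilirubin elevations occur". Table 3, footnote j, asks for the same in extended treatment.

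For adverse events of special interest (AESIs), SAP section 18.1.6 takes the centres' entries and states that "Biostatistics will not programmatically verify the AEs meeting CTCAE criteria".

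**The concern.** A lead-in that says *scheduled* is right for by-visit means and plots. It is wrong for a table meant to show the worst grade a patient reached, because it discards the samples taken in response to a rising liver test. Those samples are not a random extra. They are drawn because something is already abnormal, so they are where a peak is most likely to be seen.

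At stake is whether the laboratory tables state hepatic severity correctly, in a study that gives the liver its own management algorithm (Appendix 3) and its own advisory committee (the HAC). A programmer who follows section 18.2 and one who follows section 6.4 would also produce different tables from the same data.

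**Working it through.** The plan gives no figure to reproduce. The check sets the texts side by side and then follows one patient through them.

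**1. Which results each text admits**

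| Output | SAP 18.2 lead-in | SAP 6.4 | Protocol 8.9.3 |
|---|---|---|---|
| By-visit statistics and plots | Scheduled | Nominal visit only | By visit |
| Incidence of CTCAE abnormalities | Scheduled | Not named; the worst-case clause could apply | Treatment-emergent includes unscheduled |
| Shift by CTC grade | Scheduled | Unscheduled values contribute | Visible text describes only a reference-range shift, by visit |
| Listings | Scheduled, if read literally | All results | By-patient listings of the liver thresholds |

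The texts agree on the first row only. On CTCAE incidence, section 18.2 conflicts with the protocol. On CTC shift, it conflicts with section 6.4.

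**2. Is the change declared?** SAP section 3.3 lists departures from the protocol. Its visible text does not include a restriction to scheduled samples.

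**3. Is the word shared boilerplate?** The matching lead-ins for ECG (SAP 18.3) and vital signs (SAP 18.4) do not contain it.

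**4. Numerator and denominator.** For criteria that do not involve change from baseline, SAP section 18.2.3 says that "to be evaluable the patient need only have one post-dose value recorded". It does not repeat the scheduled limit. Read with the 18.2 lead-in, a patient could enter the denominator on an unscheduled sample that is not allowed to enter the numerator.

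**5. Direction.** Let S be a patient's scheduled post-baseline results and U the unscheduled ones. The worst grade over S cannot exceed the worst grade over S and U together. Leaving U out therefore lowers a patient's worst grade or leaves it unchanged, and the same holds for the number of patients at or above any grade.

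**6. One patient.** Assume a normal baseline ALT. The SAP 18.2.3 table puts above 3.0 to 5.0 times ULN at grade 2 and above 5.0 to 20.0 times ULN at grade 3.

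- Day 56, scheduled: 3.5 times ULN, grade 2.
- Day 60, unscheduled: 8 times ULN, grade 3.
- Day 70 onward: below 3 times ULN.

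In SAP section 6.5, Visit 14 covers Days 53 to 59 and Visit 15 covers Days 67 to 73, so Day 60 lies in no window and cannot be assigned to a scheduled visit. Under the 18.2 lead-in the worst grade is 2. With all results it is 3.

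**7. Room for this to happen.** By the same windows, the following days between Day 1 and Day 90 lie in no visit window: Day 2 (1 day), Days 31 to 32 (2), Day 38 (1), Days 60 to 66 (7) and Days 74 to 77 (4). That is 1 + 2 + 1 + 7 + 4 = 15 days. This shows that the gap exists, not how often a peak falls in it.

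**The case against.** The best defence is that the lead-in is loose drafting. It also covers the listing, yet section 18.2 itself says "All local and central laboratory results will be listed" and section 6.4 says "Listings will include scheduled, unscheduled, retest and early discontinuation data". If the word cannot be literal for the listing, perhaps it is not literal for the incidence tables. The protocol sentence in 8.9.3 also follows directly on the liver-threshold tables and might be meant for those alone, and the protocol's reference-range shift tables are by visit in any case. This is fair, and it is why the shift part is only a possible loss. It does not settle the CTCAE incidence tables: section 6.4 does not name them, section 18.2 does, and the protocol's definition is worded for any event.

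Four stronger readings are tempting, and the documents do not support them.

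- *That liver peaks vanish from the safety results.* They remain in the listings. If the site reports them, they also appear in the AESI and SAE tables and go to the HAC. With a normal baseline, the patient in the example already meets the Appendix 3 definition of a moderate elevation on Day 56, so an AESI is mandatory. SAP 18.1.1.1 uses the worst reported severity, so the peak should show there. What is lost is the top grade in the laboratory tables.
- *That the Hy's Law and liver-threshold tables omit unscheduled values.* SAP section 18.2.4 is redacted. Its item sits under the same lead-in, but its content cannot be judged.
- *That AESI counts are wrong, or that an unreported case never reaches the HAC.* Having no check by Biostatistics is not the same as having no check. Protocol section 7.1.1 provides source data verification, section 6.4.1 makes reporting mandatory, and section 6.4.4.3 gives the HAC a periodic integrated hepatic summary as well as individual AESIs.
- *That the share of missed peaks can be read from visit spacing.* The laboratory rows of Table 1 and some of the liver-sampling text are redacted, so the spacing of liver tests is unknown.

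**Conclusion.** The point holds as a conflict in the plan with a one-way effect. Read literally, SAP section 18.2 restricts the abnormal-value and CTCAE incidence tables to scheduled samples, against protocol section 8.9.3, and the CTC-grade shift tables too, against SAP section 6.4. Where this changes a patient's worst grade, it can only lower it. The worked patient moves from grade 3 to grade 2, given a normal baseline and a peak that falls outside every visit window. The number of patients affected cannot be estimated from the documents. The conclusion rests on the lead-in meaning what it says and on no change being declared in the redacted parts of SAP section 3.3. The missing AESI check is a secondary point: it leaves an unreported elevation without an automatic catch, but it is not evidence that one will be missed.

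**What to change.** In SAP section 18.2, confine *scheduled* to the by-visit descriptive statistics and plots. State that abnormal-value incidence, CTCAE incidence, worst-grade shift and any liver-threshold tables use the worst post-baseline value from all scheduled and unscheduled results, in line with SAP 6.4 and protocol 8.9.3. Any shift table meant to be by visit should be labelled so. Add a central/local rule for these tables: the present preference for the central result is framed per visit, and an unscheduled sample may have only a local result. Use the same set of results for numerator and denominator.

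As a secondary check in SAP section 18.1.6, derive the laboratory parts of the Appendix 3 moderate and major elevations from the data, list any that have no matching AESI record, and query them before database lock.

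The cost is a few sentences and modest programming on data already collected. Reported abnormality rates may rise.

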18.2.1. LABORATORY SPECIFIC DERIVATIONS

Cockcroft-Gault (CG) formula for Creatinine clearance derivation:

Formula for male: $CrCl = [(140 - \text{age in years}) \times (\text{Weight in kg})] / (72 \times Cr)$

Formula for female: $CrCl = [(140 - \text{age in years}) \times (\text{Weight in kg}) \times 0.85] / (72 \times Cr)$

Cr (serum creatinine) = mg/dL [need to make sure Cr is provided on mg/dL (and if not a conversion will be needed)] as specified.

18.2.2. WEIGHT COLLECTED AT EACH VISIT AND AGE BASED ON CRF.LABORATORY REFERENCE RANGES

Quantitative laboratory measurements will be compared with the relevant laboratory reference ranges in SI units and categorized as:

- Low: Below the lower limit of the laboratory reference range.
- Normal: Within the laboratory reference range (upper and lower limit included).
- High: Above the upper limit of the laboratory reference range.

18.2.3. CTC GRADING FOR LABORATORY DATA

Laboratory measurements will be graded using the Common Toxicity grading (CTCAE v5.0) system as defined in the following link:

https://ctep.cancer.gov/protocolDevelopment/electronic_applications/docs/CTCAE_v5_Quick_Reference_8.5x11.pdf

CTCAE grading that will be used is summarized in the below:

Document:	\\weedc-vnasc01\BIOSdata\F2G\F901318\		
Author:		Version Number:	3.0
		Version Date:	06Apr2023
Template No.:	CS_TP_BS016 Revision 6	Reference:	CS_WI_BS005
Effective Date:	02Dec2019		

F2G Ltd.
PROTOCOL F901318/0032

CTCAE Term	Laboratory Test	Grade 1	Grade 2	Grade 3	Grade 4	Grade 5
Anemia	Hemoglobin (g/L)	Hemoglobin (Hgb) <LLN - 10.0 g/dL; <LLN - 6.2 mmol/L; <LLN - 100 g/L	Hgb <10.0 - 8.0 g/dL; <6.2 - 4.9 mmol/L; <100 - 80g/L	Hgb <8.0 g/dL; <4.9 mmol/L; <80 g/L; transfusion indicated	Life-threatening consequences; urgent intervention indicated	Death
Hemoglobin increased	Hemoglobin (g/L)	Increase in >0 - 2 g/dL	Increase in >2 - 4 g/dL	Increase in >4 g/dL	-	-
Platelet count decreased	Platelet count (x10E9/L)	<LLN - 75,000/mm3; <LLN - 75.0 x 10e9 /L	<75,000 - 50,000/mm3; <75.0 - 50.0 x 10e9 /L	<50,000 - 25,000/mm3; <50.0 - 25.0 x 10e9 /L	<25,000/mm3 ; <25.0 x 10e9 /L	-
Disseminated intravascular coagulation	Platelet count (x10E9/L)	-	Laboratory findings with no bleeding	Laboratory findings and bleeding	Life-threatening consequences; urgent intervention indicated	Death
White blood cell (WBC) decreased	WBC (x 10E9/L)	<LLN - 3000/mm3; <LLN - 3.0 x 10e9 /L	<3000 - 2000/mm3; <3.0 - 2.0 x 10e9 /L	<2000 - 1000/mm3; <2.0 - 1.0 x 10e9 /L	<1000/mm3; <1.0 x 10e9 /L	-

Document: \\weedc-vnasc01\BIOSdata\F2G\F901318\

Author:

Version Number:

3.0

Version Date:

06Apr2023

Template No.: CS_TP_BS016 Revision 6

Reference: CS_WI_BS005

Effective Date: 02Dec2019

F2G Ltd.
PROTOCOL F901318/0032

CTCAE Term	Laboratory Test	Grade 1	Grade 2	Grade 3	Grade 4	Grade 5
Leukocytosis	WBC (x 10E9/L)	-	-	>100,000/mm ³	Clinical manifestations of leucostasis; urgent intervention indicated	Death
Neutrophils count decreased	Absolute neutrophils count (x 10E9/L)	<LLN - 1500/mm ³ ; <LLN - 1.5 x 10e9 /L	<1500 - 1000/mm ³ ; <1.5 - 1.0 x 10e9 /L	<1000 - 500/mm ³ ; <1.0 - 0.5 x 10e9 /L	<500/mm ³ ; <0.5 x 10e9 /L	-
Hypernatremia	Sodium (mmol/L)	>ULN - 150 mmol/L	>150 - 155 mmol/L; intervention initiated	>155 - 160 mmol/L; hospitalization indicated	>160 mmol/L; life-threatening consequences	Death
Hyponatremia	Sodium (mmol/L)	<LLN - 130 mmol/L	125-129 mmol/L and asymptomatic	125-129 mmol/L symptomatic; 120-124 mmol/L regardless of symptoms	<120 mmol/L; life-threatening consequences	Death
Hyperkalemia	Potassium (mmol/L)	>ULN - 5.5 mmol/L	>5.5 - 6.0 mmol/L; intervention initiated	>6.0 - 7.0 mmol/L; hospitalization indicated	>7.0 mmol/L; life-threatening consequences	Death

Document: \\weedc-vnasc01\BIOSdata\F2G\F901318\ [Redacted]
 Author: [Redacted] Version Number: 3.0
 Version Date: 06Apr2023
 Template No.: CS_TP_BS016 Revision 6 Reference: CS_WI_BS005
 Effective Date: 02Dec2019

F2G Ltd.
PROTOCOL F901318/0032

CTCAE Term	Laboratory Test	Grade 1	Grade 2	Grade 3	Grade 4	Grade 5
Hypokalemia	Potassium (mmol/L)	≥ 3.0 mmol/L – < LLN	n/a	≥ 2.5 - < 3.0 mmol/L	< 2.5 mmol/L	n/a
Hypercalcemia	Calcium (mmol/L)	Corrected serum calcium of >ULN - 11.5 mg/dL; >ULN - 2.9 mmol/L; Ionized calcium >ULN - 1.5 mmol/L	Corrected serum calcium of >11.5 - 12.5 mg/dL; >2.9 - 3.1 mmol/L; Ionized calcium >1.5 - 1.6 mmol/L; symptomatic	Corrected serum calcium of >12.5 - 13.5 mg/dL; >3.1 - 3.4 mmol/L; Ionized calcium >1.6 - 1.8 mmol/L; hospitalization indicated	Corrected serum calcium of >13.5 mg/dL; >3.4 mmol/L; Ionized calcium >1.8 mmol/L; life-threatening consequences	Death
Hypocalcemia	Calcium (mmol/L)	Corrected serum calcium of <LLN - 8.0 mg/dL; <LLN - 2.0 mmol/L; Ionized calcium <LLN - 1.0 mmol/L	Corrected serum calcium of <8.0 - 7.0 mg/dL; <2.0 - 1.75 mmol/L; Ionized calcium <1.0 - 0.9 mmol/L; symptomatic	Corrected serum calcium of <7.0 - 6.0 mg/dL; <1.75 - 1.5 mmol/L; Ionized calcium <0.9 - 0.8 mmol/L; hospitalization indicated	Corrected serum calcium of <6.0 mg/dL; <1.5 mmol/L; Ionized calcium <0.8 mmol/L; life-threatening consequences	Death

Document: \\weedc-vnasc01\BIOSdata\F2G\F901318\ [Redacted]
 Author: [Redacted] Version Number: 3.0
 Version Date: 06Apr2023
 Template No.: CS_TP_BS016 Revision 6 Reference: CS_WI_BS005
 Effective Date: 02Dec2019

F2G Ltd.
PROTOCOL F901318/0032

CTCAE Term	Laboratory Test	Grade 1	Grade 2	Grade 3	Grade 4	Grade 5
Hyperglycemia	Glucose (mmol/L)	Abnormal glucose above baseline with no medical intervention	Change in daily management from baseline for a diabetic; oral antidiabetic agent initiated; workup for diabetes	Insulin therapy initiated; hospitalization indicated	Life-threatening consequences; urgent intervention indicated	Death
Hypoglycemia	Glucose (mmol/L)	<LLN - 55 mg/dL; <LLN - 3.0 mmol/L	<55 - 40 mg/dL; <3.0 - 2.2 mmol/L	<40 - 30 mg/dL; <2.2 - 1.7 mmol/L	<30 mg/dL; <1.7 mmol/L; life-threatening consequences; seizures	Death
Glucose intolerance	Glucose (mmol/L)	Asymptomatic; clinical or diagnostic observations only; intervention not indicated	Symptomatic; dietary modification or oral agent indicated	Severe symptoms; insulin indicated	Life-threatening consequences; urgent intervention indicated	Death
Creatinine increased	Creatinine (µmol/L)	>ULN - 1.5 x ULN	>1.5 - 3.0 x baseline; >1.5 - 3.0 x ULN	>3.0 x baseline; >3.0 - 6.0 x ULN	>6.0 x ULN	-

Document: \\weedc-vnasc01\BIOSdata\F2G\F901318\ [Redacted]

Author: [Redacted] Version Number: 3.0

Version Date: 06Apr2023

Template No.: CS_TP_BS016 Revision 6

Reference: CS_WI_BS005

Effective Date: 02Dec2019

F2G Ltd.
PROTOCOL F901318/0032

CTCAE Term	Laboratory Test	Grade 1	Grade 2	Grade 3	Grade 4	Grade 5
Alkaline phosphatase (ALP) increased	ALP (U/L)	>ULN - 2.5 x ULN if baseline was normal; 2.0 - 2.5 x baseline if baseline was abnormal	>2.5 - 5.0 x ULN if baseline was normal; >2.5 - 5.0 x baseline if baseline was abnormal	>5.0 - 20.0 x ULN if baseline was normal; >5.0 - 20.0 x baseline if baseline was abnormal	>20.0 x ULN if baseline was normal; >20.0 x baseline if baseline was abnormal	-
Alanine aminotransferase (ALT) increased	ALT (U/L)	>ULN - 3.0 x ULN if baseline was normal; 1.5 - 3.0 x baseline if baseline was abnormal	>3.0 - 5.0 x ULN if baseline was normal; >3.0 - 5.0 x baseline if baseline was abnormal	>5.0 - 20.0 x ULN if baseline was normal; >5.0 - 20.0 x baseline if baseline was abnormal	>20.0 x ULN if baseline was normal; >20.0 x baseline if baseline was abnormal	-
Aspartate transaminase (AST) increased	AST (U/L)	>ULN - 3.0 x ULN if baseline was normal; 1.5 - 3.0 x baseline if baseline was abnormal	>3.0 - 5.0 x ULN if baseline was normal; >3.0 - 5.0 x baseline if baseline was abnormal	>5.0 - 20.0 x ULN if baseline was normal; >5.0 - 20.0 x baseline if baseline was abnormal	>20.0 x ULN if baseline was normal; >20.0 x baseline if baseline was abnormal	-

Document: \\weedc-vnasc01\BIOSdata\F2G\F901318\

Author:

Version Number:

3.0

Version Date:

06Apr2023

Template No.: CS_TP_BS016 Revision 6

Reference: CS_WI_BS005

Effective Date: 02Dec2019

F2G Ltd.
PROTOCOL F901318/0032

CTCAE Term	Laboratory Test	Grade 1	Grade 2	Grade 3	Grade 4	Grade 5
Blood bilirubin increased	Total bilirubin (μmol/L)	>ULN - 1.5 x ULN if baseline was normal; > 1.0 - 1.5 x baseline if baseline was abnormal	>1.5 - 3.0 x ULN if baseline was normal; >1.5 - 3.0 x baseline if baseline was abnormal	>3.0 - 10.0 x ULN if baseline was normal; >3.0 - 10.0 x baseline if baseline was abnormal	>10.0 x ULN if baseline was normal; >10.0 x baseline if baseline was abnormal	-
CPK increased	Creatine phosphokinase	>ULN - 2.5 x ULN	>2.5 x ULN - 5 x ULN	>5 x ULN - 10 x ULN	>10 x ULN	-
Creatinine increased	Creatinine	>ULN - 1.5 x ULN	>1.5 - 3.0 x baseline; >1.5 - 3.0 x ULN	>3.0 x baseline; >3.0 - 6.0 x ULN	>6.0 x ULN	-
Gamma glutamyl transferase (GGT) increased	GGT (U/L)	>ULN - 2.5 x ULN if baseline was normal; 2.0 - 2.5 x baseline if baseline was abnormal	>2.5 - 5.0 x ULN if baseline was normal; >2.5 - 5.0 x baseline if baseline was abnormal	>5.0 - 20.0 x ULN if baseline was normal; >5.0 - 20.0 x baseline if baseline was abnormal	>20.0 x ULN if baseline was normal; >20.0 x baseline if baseline was abnormal	-
Hypoalbuminemia	Albumin (g/L)	<LLN - 3 g/dL; <LLN - 30 g/L	<3 - 2 g/dL; <30 - 20 g/L	<2 g/dL; <20 g/L	Life-threatening consequences; urgent intervention indicated	Death

Document: \\weedc-vnasc01\BIOSdata\F2G\F901318\

Author:

Version Number:

3.0

Version Date:

06Apr2023

Template No.: CS_TP_BS016 Revision 6

Reference: CS_WI_BS005

Effective Date: 02Dec2019

F2G Ltd.
PROTOCOL F901318/0032

CTCAE Term	Laboratory Test	Grade 1	Grade 2	Grade 3	Grade 4	Grade 5
Activated partial thromboplastin time prolonged	Prothrombin time and activated Partial Thromboplastin Time	>ULN - 1.5 x ULN	>1.5 - 2.5 x ULN	>2.5 x ULN; bleeding	-	-
Hepatic failure		-	-	Asterixis; mild encephalopathy; drug-induced liver injury (DILI); limiting self care ADL	Life-threatening consequences; moderate to severe encephalopathy; coma	Death
INR increased	Prothrombin time and activated Partial Thromboplastin Time	>1.2 - 1.5; >1 - 1.5 x baseline if on anticoagulation; monitoring only indicated	>1.5 - 2.5; >1.5 - 2.5 x baseline if on anticoagulation; dose adjustment indicated	>2.5; >2.5 x baseline if on anticoagulation; bleeding	-	-

Predefined treatment-emergent abnormalities, as defined by CTCAE criteria, will be presented in tables where the incidence rate will be based on the total number of patients ‘at risk’, for example:

- If a CTCAE criterion involves a change from baseline, evaluable patients would have both a pre-dose and at least one post-dose value recorded.
- If a CTCAE criterion does not consider change from baseline, to be evaluable the patient need only have one post-dose value recorded.

Document: \\weedc-vnasc01\BIOSdata\F2G\F901318\ [Redacted]
 Author: [Redacted] Version Number: 3.0
 Version Date: 06Apr2023
 Template No.: CS_TP_BS016 Revision 6 Reference: CS_WI_BS005
 Effective Date: 02Dec2019

[Redacted]

F2G Ltd.
PROTOCOL F901318/0032

In the event that a laboratory value does not comply with the CTCAE criterion, the laboratory value will be categorised as normal.

18.2.4. [Redacted]

[Redacted]

[Redacted]

[Redacted]

[Redacted]

[Redacted]

[Redacted]

[Redacted]

[Redacted]

Document: \\eedc-vnasc01\BIOSdata\F2G\F901318 [Redacted]

Author: [Redacted] Version Number: 3.0

Version Date: 06Apr2023

Template No.: CS_TP_BS016 Revision 6

Reference: CS_WI_BS005

Effective Date: 02Dec2019

[Redacted]

[REDACTED]

F2G Ltd.
PROTOCOL F901318/0032

[REDACTED]

[REDACTED]

[REDACTED]

[REDACTED]

